2.3 Non-Amgen Medicinal Product Background

2.3.1 Cinacalcet

Cinacalcet is a first-in-class calcimimetic agent that functions as an allosteric modulator of the CaR on the surface of parathyroid cells, increasing the sensitivity of the CaR to extracellular calcium ions.

Cinacalcet has been approved by the Food and Drug Administration in the United States for the treatment of SHPT in patients with CKD on dialysis, for the treatment of hypercalcemia in subjects with parathyroid carcinoma, and for the treatment of severe hypercalcemia in patients with primary HPT who are unable to undergo parathyroidectomy. Cinacalcet also has received marketing authorization under the name of Sensipar, Mimpara, or Regpara, in 6 countries in Asia, Australia, Canada, multiple countries in Europe, parts of Latin America, several countries in the Middle East, New Zealand, and Russia. As of 07 September 2012, cinacalcet has been approved in 60 countries. Please refer to the [cinacalcet package insert](#) for the exact approved indication(s) in each of these regions.

In adult humans, the maximum observed plasma concentration (C_{max}) of cinacalcet is achieved between 2 to 6 hours after oral doses, which corresponds temporally with the nadir in plasma PTH. After absorption, cinacalcet concentrations in serum decrease in a biphasic fashion with a terminal half-life of 30 to 40 hours. Steady-state drug levels are achieved within 7 days, and serum calcium concentrations remain constant over the 24-hour dosing interval once stable serum drug levels are achieved in patients with CKD on hemodialysis. Cinacalcet is metabolized extensively by multiple hepatic cytochrome P-450 (CYP) enzymes, and < 1% of the parent drug is excreted in the urine. No unique metabolites of cinacalcet have been identified in humans (original NDA 21-688, Study 980233).

Approved

An extensive phase 3 program was completed by Amgen in adult non-transplant subjects with end-stage renal disease (ESRD), demonstrating that treatment with cinacalcet resulted in concurrent reductions in PTH, calcium, P, and Ca x P, among dialysis subjects with inadequately controlled SHPT as defined by baseline plasma PTH > 300 pg/mL (31.8 pmol/L). The incidence of serious adverse events was 31% and 29% among subjects assigned randomly to treatment with cinacalcet or placebo. The most common adverse events were nausea (31% versus 19%) and vomiting (27% versus 15%) among subjects assigned to treatment with cinacalcet compared with placebo. Post-hoc analyses of phase 3 clinical trial data demonstrated that treatment with cinacalcet enabled a significantly greater proportion of adult subjects on dialysis with SHPT to achieve National Kidney Foundation- Kidney Disease Outcomes Quality Initiative (NKF-K/DOQI)TM recommended targets for PTH, calcium, P, and Ca x P compared with treatment using traditional therapies for SHPT ([Moe et al, 2005](#)).

Please refer to the [Cinacalcet package insert](#) for Sensipar/Mimpara/Regpara for additional detailed information about the chemistry, toxicology, preclinical pharmacology, PK, safety, and clinical experience of cinacalcet.

2.4 Rationale

Sub-optimal adherence and compliance with oral medication regimens that include cinacalcet are common among patients managed with hemodialysis. This is due in part to a high daily pill burden and gastrointestinal intolerance in such individuals, and the overall complexity of the drug treatment strategies used to manage them clinically. Etelcalcetide is administered intravenous (IV) at the end of each hemodialysis session, and thus provides the opportunity to circumvent the shortcomings of oral therapies and to achieve greater drug adherence/compliance for managing SHPT.

This current study is designed to assess the efficacy and safety of a novel therapeutic agent, IV etelcalcetide, compared with the other calcimimetic agent (oral cinacalcet), for the treatment of SHPT in CKD subjects on hemodialysis. The data from this study will be used to support registration of etelcalcetide in China and other countries.

2.5 Clinical Hypotheses

Treatment of SHPT with etelcalcetide is not inferior to treatment with cinacalcet as measured by the proportion of subjects with > 30% reduction in predialysis serum PTH levels from baseline during EAP.

Treatment with etelcalcetide is superior to treatment with cinacalcet as measured by the proportion of subjects with > 50% decrease in predialysis serum PTH from baseline, and by the proportion of subjects with > 30% decrease in predialysis serum PTH from baseline during EAP.

3. EXPERIMENTAL PLAN

3.1 Study Design

This is a phase 3, multicenter, randomized, active-controlled, double-blind, double-dummy, dose-titration, 26-week treatment period comparison of etelcalcetide and cinacalcet.

All subjects, regardless of treatment assignment, may receive standard of care as prescribed by the individual Investigator, with calcium supplements, phosphate binders, vitamin D sterols, and nutritional vitamin D supplements. If treatment with calcitriol or vitamin D analogs is ongoing when subjects are enrolled in the study, the doses of these agents should remain constant for the duration of study, unless treatment with vitamin D is initiated, interrupted, or adjusted for reasons of safety.

Subjects will be stratified by screening serum PTH level (< 900 pg/mL, \geq 900 pg/mL) ($< 95.40 \text{ pmol/L}$, $\geq 95.40 \text{ pmol/L}$), screening serum cCa ($\geq 9.0 \text{ mg/dL}$, $< 9.0 \text{ mg/dL}$) ($\geq 2.25 \text{ mmol/L}$, $< 2.25 \text{ mmol/L}$) measured by the central laboratory, and country (China versus non-China), and be randomized 1:1 to receive etelcalcetide or cinacalcet.

The overall study design is described by a [study schema](#) at the end of the protocol synopsis section.

The study endpoints are defined in [Section 10.1.1](#).

3.2 Number of Sites

The study is planned to be conducted at approximately 120 centers in China **mainland**, Taiwan, South Korea, Hong Kong, Malaysia, and India. Other countries **and/or regions** may be added as needed.

Sites that do not enroll subjects within 3 months of site initiation may be closed.

3.3 Number of Subjects

Participants in this clinical investigation shall be referred to as “subjects.”

Approximately 660 subjects will be randomized in this study (approximately 330 subjects in each of the 2 treatment arms). Refer to [Section 10.2](#) for sample size considerations.

3.4 Replacement of Subjects

Randomized subjects who subsequently withdraw from the study will not be replaced.

3.5 Estimated Study Duration

3.5.1 Study Duration for Subjects

The maximum duration of study participation for a subject will be approximately 9 months; which includes an 8-week screening period, a 26-week treatment period, and a 30-day follow-up safety visit that is considered the end-of-study (EOS) visit.

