Non-Amgen Investigational Product Dosage and Administration: Subjects who are randomized to treatment with oral cinacalcet will be treated with oral IP daily and three times weekly IV doses of placebo at the end of each dialysis session, for 26 weeks. The starting dose of oral IP is 25 mg and will be titrated by the IVR/IWR to target predialysis [REDACTED]

[REDACTED] The minimum oral IP dose is 25 mg, and the maximum dose is 100 mg. The dose of oral IP may be increased in increments of 25 mg at weeks 5, 9, 13, and 17, if PTH values remain $> 300 \text{ pg/mL (31.80 pmol/L)}$ and cCa values remain $\geq 8.3 \text{ mg/dL (2.07 mmol/L)}$ based on results **measured by the central laboratory** obtained the previous or current week.

Procedures: After signing the informed consent form, subjects will enter the screening period (up to 8 weeks). Screening evaluations will include review of inclusion/exclusion criteria, demographics, medical history, prior and concomitant medications, physical examination, electrocardiogram, and reporting of serious adverse events. Blood samples will be collected for pharmacokinetics (PK), hematology, chemistry, PTH, and for all females of childbearing potential a serum pregnancy test. Kt/V or URR assessment will be performed at screening unless a qualifying Kt/V or URR measurement from within 4 weeks prior to screening assessments is available. At the day 1 visit, baseline assessments will be performed and eligible subjects will be enrolled and randomized 1:1 to either etelcalcetide or cinacalcet into the 26-week treatment period and should receive the first dose of IP within 1 day of randomization. Randomization will be stratified by PTH level ($< 900 \text{ pg/mL, } \geq 900 \text{ pg/mL}$) ($< 95.40 \text{ pmol/L, } \geq 95.40 \text{ pmol/L}$), screening serum cCa ($\geq 9.0 \text{ mg/dL, } < 9.0 \text{ mg/dL}$) ($\geq 2.25 \text{ mmol/L, } < 2.25 \text{ mmol/L}$), both **measured by the central laboratory**, and country (China versus non-China). Assessments during the treatment period should be performed during the designated study week on the same hemodialysis treatment day of the week as the day dosing was started and will be scheduled based on the day 1 date. Subjects will complete the study at the follow-up visit 30 days (± 3 days) after the last dose of IP. IP will be dosed to achieve predialysis [REDACTED]

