6.5.5 Allowed Treatments and/or Procedures During a Study Period

- Subjects should be on maintenance hemodialysis treatment with a prescription for dialysis 3 times per week. Dialysis duration and membrane may be modified to maintain adequate hemodialysis treatment (eg, Kt/V \geq 1.2 or URR > 65%). If a subject requires a significant change in hemodialysis prescription to maintain adequate hemodialysis (eg, permanent change from TIW), then the subject will be discontinued from treatment with IP, and every effort will be made to continue to follow the subject through the duration of the study.
- Intermittent additional hemodialysis treatment (eg, for ultrafiltration) or changes in hemodialysis schedule (eg, missed/rescheduled treatments or shifts in schedule) are not considered significant changes in hemodialysis treatment prescription.
- Subjects must have a prescribed dialysate calcium concentration \geq 2.5 mEq/L (1.25 mmol/L) stable for at least 4 weeks prior to screening laboratories, and the dialysate calcium concentration must be maintained \geq 2.5 mEq/L (1.25 mmol/L) throughout the study.
- Medications used to treat hemodialysis-related symptoms or comorbid conditions should be reported as concomitant medications whenever administered to the subject.
- Medications administered at each dialysis session (eg, heparin, diphenhydramine) should be reported on the eCRF with a frequency of 3 times per week unless a change in dose or frequency occurs. The following medications used in the delivery of hemodialysis should not be reported on the eCRF as concomitant medication:
 - local anesthetic for cannulation
 - saline prime for the dialysis circuit
 - saline or hypertonic saline for management of intradialytic hypotension
 - oxygen

Approved

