	18	19	20	21	22	23	24	25	26	27 ^b			
IV investigational product administration				Three times per week at the end of the hemodialysis session ending at week 26									
Dose titration ^c													
Informed Consent													
Inclusion/ Exclusion													
Medical History													
Demographics													
Prior & Concomitant Medication	X	X	X	X	X	X	X	X	X	X	X	X	
Physical Examination											X	X	
Randomization													
Dispensation of oral IP bottle				X				X					
Pill count	X		X		X		X	X	X			X	
TIW Admin of IV IP (by site staff at the end of hemodialysis) ^d	X	X	X	X	X	X	X	X	X				
Adverse events ^e	X	X	X	X	X	X	X	X	X	X	X	X	
Vital status ^f									X			X	
Prior to dialysis													
ECG ^g										X		X	
Serum pregnancy test ^h						X					X	X	
Hematology											X	X	
Chemistry											X	X	
Albumin, Ca ^{ij}	X		X		X		X		X	X			X ^d
Phosphorus			X			X		X	X				
PTH	X	X	X		X		X		X	X	X	X	
PK ^k								X		X			
25(OH)D													
ADA											X	X	
After dialysis													
Pulse and blood pressure ^L									X			X	
Height													
Weight									X			X	
PK (10-30 min post dose) ^{ik}							X						

Footnotes defined on the next page

Approved

ADA = antidrug antibody; [REDACTED]; cCa = correct calcium; Ca = calcium; [REDACTED]; ECG = electrocardiogram;

IP = investigational product; IV = intravenous; PTH = parathyroid hormone, PK = pharmacokinetic; TIW = three times per week

^a Assessments during the Treatment Period should be performed during the designated study week on the same hemodialysis treatment day of the week as the day dosing was started whenever possible.

^b Week 27 assessments should be performed on the day of the first hemodialysis treatment after the last dose of IP.

^c The dose of IP may be decreased at any time.

^d When dosing with IP is suspended for cCa < 7.5 mg/dL (**1.87 mmol87mmol/L**), a predialysis serum sample for albumin and calcium should be submitted to the central laboratory on the day dosing is suspended. Dose suspension samples do not need to be collected if a routine, local chemistry or albumin/calcium/P sample is obtained on the same day.

^e After informed consent and before first dose of IP, only serious adverse events are to be reported. Subjects will be followed for both adverse events and serious adverse events for 30 days after the last dose of IP.

^f Vital status will only be appropriately ascertained by sites for subjects who early terminated the study.

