7.2.4 Follow-up Visit

Subjects will complete the follow-up visit 30 days (\pm 3 days) after the last dose of IP. If a subject early terminates from IP or the study, the follow-up visit should also occur within 30 days (\pm 3 days) after the last dose of IP.

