8.3 Reasons for Removal From Procedures, Treatment, or Study

8.3.1 Reasons for Removal From Treatment

Reasons for removal from protocol-required IP(s) or procedural assessments include any of the following:

- **Protocol Specified Criteria**
 - subject requires a significant permanent change in hemodialysis prescription to maintain adequate hemodialysis
 - subject receives a kidney transplant
 - subject undergoes a parathyroidectomy
- **Ineligibility determined**
- **Protocol deviation**
- **Noncompliance**
- Subject request
- **Adverse event**
- Death
- Lost to follow-up
- Decision by Sponsor (other than subject request, safety concern, lost to follow-up)

Approved

Subjects who are removed from protocol-required IP(s) will be approached by investigators to determine the amount of follow-up assessments but at a minimum for vital status at the week 26.

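### The protocol does not say consistently whether a subject who stops IP early stays in the study, and it never makes weeks 20-27 PTH the default follow-up for that subject

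*Protocol*

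**What the plan says.** Some passages read as if the study ends 30 days after the last dose:

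- Protocol 3.5.1 describes "a 30-day follow-up safety visit that is considered the end-of-study (EOS) visit".
- Synopsis, Procedures: "Subjects will complete the study at the follow-up visit 30 days (± 3 days) after the last dose of IP".
- Protocol 7.2.4: "If a subject early terminates from IP or the study, the follow-up visit should also occur within 30 days" (± 3 days) of the last dose.
- Protocol 8.3.1: subjects removed from IP are asked how much follow-up they accept, "but at a minimum for vital status at the week 26".

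Other passages read as if participation continues:

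- Protocol 6.5.5, for a stop caused by a changed dialysis prescription: "every effort will be made to continue to follow the subject through the duration of the study".
- Protocol 7.2.5 lets a subject off IP remain in the study, at a level of follow-up that may vary.
- Protocol 8.1 requires the investigator to discuss continuing the schedule and collecting endpoint data.
- Protocol 8.3.2 does not list stopping IP among the reasons for removal from study.
- The protocol glossary and SAP 5.1 end a subject's study at the last procedure or assessment.
- Protocol 3.5.2 allows for a primary-endpoint assessment later than the follow-up visit.
- Protocol 12.4 makes the investigator responsible for protocol-stipulated assessments, including in subjects not on therapy.

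On the analysis side, SAP 9.5.1.1 uses any PTH value in the EAP. With none, it imputes response at 60% for cinacalcet and 48% for etelcalcetide. Protocol 10.5.3 and 10.5.3.1 count a subject without EAP values as a non-responder for the two superiority endpoints and for phosphorus.

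**The concern.** The FAS analysis calls for an EAP measurement whether or not the subject is still on drug, and falls back on imputation only when there is none. The follow-up rules do not reliably produce that measurement after a permanent stop. Protocol 6.2.3 says that scheduled assessments are still completed during a dose suspension. Nothing equivalent covers permanent discontinuation, where the amount of follow-up is left to agreement and the stated floor omits the primary measurement.

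Two sites could therefore treat identical patients differently. One closes the subject at the 30-day visit and later records vital status. The other continues the schedule and draws PTH in weeks 20-27. In the first case an outcome that might have been measured is replaced by an assumed one, in patients who would generally still be attending dialysis. Part of the all-randomised comparison would then rest on assumption instead of data.

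**Working it through.** **The plan's own figures.** Protocol 3.5.1 gives a maximum participation of about 9 months: 8×7 + 26×7 + 30 = 268 days, or 8.8 months. This agrees. With power = Φ[(d − 1.96·SE₀)/SE₁], where SE₀ is the pooled and SE₁ the unpooled standard error, 300 per arm gives 84.0% for 52% v 40% and 71.9% for 68% v 58%. The plan states about 84% and 72%. Non-inferiority power at 58% v 68% with a 12-point margin is above 99%, as stated.

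**When the 30-day visit precedes the EAP.** SAP 5.1 counts study weeks as 7-day periods from Study Day 1, so week k starts on day 7(k−1)+1. Week 17 starts on day 113, as in Table 2. Week 20 starts on day 7×19+1 = 134, and week 27 covers days 183-189.

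- Nominal visit: last dose + 30 < 134 gives a last dose on or before day 103 (week 15).
- Visit at 33 days: day 100 or earlier. Visit at 27 days: day 106 or earlier.
- Share of the 182-day treatment period: 103/182 = 57%.

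**An illustrative missing rate.** The documents give no rate of early IP stops. Suppose that the 10% dropout allowance in Protocol 10.2 (66 of 660) consisted entirely of IP stops, spread evenly over 182 days, and that nobody continued visits. Then 66×103/182 = 37 subjects would reach the 30-day visit before the EAP, and 37/660 = 5.6%.

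**Effect on non-inferiority.** Take 330 per arm, the same missing share m in both arms, and the planned rates among measured subjects. The cinacalcet minus etelcalcetide difference is then (1−m)(−10) + m(+12) points:

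- m = 5.6%: −9.44 + 0.67 = −8.8 points.
- m = 10%: −9.0 + 1.2 = −7.8 points.
- m = 20%: −8.0 + 2.4 = −5.6 points.

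Approximate power, treating imputed responses as if observed, is 99.95% at 10% missing and 99.6% at 20%.

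**Effect on superiority.** Under non-responder imputation each rate is multiplied by (1−m). At 330 per arm:

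| m | >50% rates | Power | >30% rates | Power |
|---|---|---|---|---|
| 0 | 52.0 v 40.0 | 87% | 68.0 v 58.0 | 76% |
| 5.6% | 49.1 v 37.8 | 84% | 64.2 v 54.8 | 70% |
| 10% | 46.8 v 36.0 | 81% | 61.2 v 52.2 | 65% |
| 20% | 41.6 v 32.0 | 73% | 54.4 v 46.4 | 54% |

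**The case against.** A reader might infer that anyone who stops before about week 15 has finished the study before the EAP opens. The documents do not support that. Protocol 7.2.5 and 8.1 allow participation to continue, 8.3.2 does not treat an IP stop as removal from study, and 12.4 keeps the investigator responsible for stipulated assessments off therapy. Section 3.5.1 gives the maximum duration with a full 26 weeks of treatment, so it can be read as describing a completer. Section 7.2.4 sets the timing of a visit and does not itself call that visit the end of study. All of this stands. What it does not do is require EAP PTH: follow-up may vary, options are discussed, and the amount is to be determined.

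A reader might also infer that the visit plan costs a known number of outcomes. It does not. The 10% is a dropout allowance and may include deaths, withdrawn consent and loss to follow-up, which no schedule can recover. The figure of 37 holds only under the assumptions given with it. Nor do the documents say whether the planned rates already count missing subjects as non-responders. If they do, part of the power loss is already in the plan.

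A third tempting reading concerns Table 3 footnote b: "Week 27 assessments should be performed on the day of the first hemodialysis treatment after the last dose of IP". Applied to someone whose last dose was in week 23, it would put the week 27 draw in week 23 or 24. That loses no outcome. Draws in weeks 20 and 22 are already scheduled, one available EAP value is enough, and weeks 23 and 24 lie inside the EAP. Since early stoppers have their own termination visit, the footnote is most naturally read as meant for completers. It needs only a clarifying phrase.

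**Conclusion.** The concern holds as an inconsistency with a practical consequence. The protocol gives conflicting signals on whether the 30-day visit ends the study for a subject who stops IP, and its only stated minimum follow-up omits the primary measurement. With a last dose on or before day 103 (100 to 106 across the visit window), a site following the synopsis, 7.2.4 and 8.3.1 collects no EAP PTH.

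Non-inferiority is not at risk: the imputation works against etelcalcetide, and power stays above 99% even at 20% missing. The exposure lies in the two superiority tests. The >30% test has the lower planned power of the two and, in the illustration, loses more of it at each missing rate. The size is conditional on an unknown missing rate, equal missingness in the arms, and planned rates that describe measured subjects. The change is worth making because it is cheap and replaces assumed outcomes with measured ones.

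**What to change.** Reconcile the passages in the synopsis and in Protocol 3.5.1, 7.2.4, 7.2.5 and 8.3.1:

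- Call the 30-day visit a safety visit.
- For subjects who stop IP without withdrawing consent, set end of study at the later of calendar week 27 (days 183-189) and the 30-day safety visit. The words about the later date are needed: for a last dose on day 160 or after, the safety visit falls on day 190 or later, so a plain week 27 cut-off would end the study before it.
- Make the weeks 20-27 predialysis central-laboratory draws already in Table 3 (PTH, albumin/calcium, phosphorus) the default follow-up after an IP stop. Keep vital status alone for those who decline.
- State that Table 3 footnote b applies to subjects who complete IP, and define week 27 by study day for the others.

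The cost is amendment wording and up to five extra samples per early stopper, at dialysis sessions already attended. Some subjects will decline, so imputation is still needed, but for fewer people.

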3.5.2 End of Study

Primary Completion: The primary completion date is when the last subject is assessed or receives an intervention for evaluation in the study at the follow-up visit (30 days after last dose [\pm 3 days]) or the last assessment is collected for the primary endpoint, whichever is later.

End of Study: The end of study date is defined as the date when the last subject is assessed or receives an intervention for evaluation in the study (ie, last subject last visit), following any additional parts in the study (eg, long-term follow-up) as applicable.

